12.2 Participant demographics and other baseline characteristics

Demographic and other baseline data will be listed and summarized descriptively by treatment for all participants. Categorical data will be presented as frequencies and percentages. For continuous data, mean, standard deviation, median, minimum, and maximum will be presented. All demographic data and data on other baseline characteristics (e.g., alcohol, HIV and hepatitis screening etc.) will be listed by treatment and participant in detail. Relevant medical history, current medical conditions, results of laboratory screens, and any other relevant information will be listed by treatment and participant.

12.3 Treatments

Dose administration will be listed by treatment arm, date and time.

Concomitant medications and significant non-drug therapies prior to and after the start of the study treatment will be listed and summarized according to the Anatomical Therapeutic Chemical (ATC) classification system by treatment.

12.4 Analysis of the primary endpoint(s)/estimand(s)

The primary endpoint is *Cryptosporidium* infection (detection of oocysts in fecal samples by EIA CCI at \geq 72 hours post-administration or sooner if associated with symptoms suggestive of diarrheal illness) up to Day 10 (inclusive). The 10 day observation window may be extended as described in Section 4.1.

12.4.1 Statistical model, hypothesis, and method of analysis

The number and proportion (in percentage) of participants with *Cryptosporidium* infection will be summarized. The lower limit of the 1-sided 80% exact confidence interval of the proportions will also be reported.

12.4.2 Supplementary analysis

Not applicable.

12.5 Analysis of secondary endpoints/estimands

The secondary endpoints include the presence of clinical symptoms (diarrheal and associated symptoms) by Day 10 and Day 28 as described in Section 8.3.2, *Cryptosporidium* infection up to Day 28, time to infection and symptom on-set, time to resolution of infection and diarrheal illness, and characteristics of clinical signs and symptoms associated with diarrheal illness, as well as safety and tolerability endpoints.

12.5.1 Efficacy and/or Pharmacodynamic endpoint(s)

The number and proportion (in percentage) of participants with clinical symptoms (by Day 10 (inclusive) and Day 28) and with *Cryptosporidium* infection up to Day 28 will be summarized by treatment. The lower limit of the 1-sided 80% exact confidence interval of the proportions will be reported by treatment. The clinical symptoms are defined as diarrheal and associated gastrointestinal symptoms, evaluated from symptom onset up to Day 10. The observation window for clinical symptoms may be extended as described in Section 4.1.

Frequency and percentage will be presented for categorical data such as grading of stool consistency and number of diarrhea episodes. Mean, standard deviation, median, minimum, and maximum will be presented for continuous data such as stool weight. On-set, duration, time to resolution of infection and diarrheal illness as well as severity of other clinical signs and symptoms associated with diarrheal illness (including but not limited to abdominal pain, abdominal cramping, nausea, vomiting, fever, electrolyte imbalance, dehydration) will be analyzed as appropriate. Details will be documented in the Statistical Analysis Plan.

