1.2 Purpose

The goal of this Phase I CHIM study will be to determine if oral administration of a Good Manufacturing Practice (GMP) supply of *C. parvum* oocysts (ABO809) to healthy volunteers results in *Cryptosporidium* infection and diarrheal illness. The study will measure fecal *Cryptosporidium* oocysts (parasitological endpoint) as well as diarrhea and associated signs and symptoms (clinical endpoint).

It is expected that approximately 90-100 percent of participants receiving ABO809 may become infected. The incidence of diarrheal illness will also be evaluated and may be somewhat lower than the incidence of infection.

This study, if successful, would enable a robust CHIM model that can be used in future studies to evaluate the efficacy of novel therapies and vaccines for the treatment and prevention of *Cryptosporidium* infection in healthy participants before they are assessed in the pediatric target population.

Amended Protocol Version v02 (Clean)

2 Objectives and endpoints

Objective(s)	Endpoint(s)		
Primary objective(s)	Endpoint(s) for primary objective(s)		
 To evaluate the incidence of Cryptosporidium infection following an oral administration of ABO809 	Cryptosporidium infection as indicated by Cryptosporidium oocysts in fecal samples measured by EIA CCI at ≥72 hours post-administration (or sooner if associated with symptoms of diarrheal illness) up to Day 10 (inclusive).		
Secondary objective(s)	Endpoint(s) for secondary objective(s)		
To evaluate the incidence and characteristics of diarrheal illness	 Presence of clinical diarrheal illness by Day 10 (inclusive) and Day 28 		
following an oral administration of ABO809	 Number of diarrhea episodes 		
	Stool weight		
	Grading of stool consistency		
	 Time to onset and time to resolution of diarrheal illness 		
	 Characteristics of clinical signs and symptoms associated with clinical diarrheal illness such as (abdominal pain, abdominal cramping, nausea, vomiting, fever, electrolyte imbalance, dehydration) up to Day 28 		
	Cryptosporidium infection as indicated by Cryptosporidium oocysts in fecal samples measured by EIA CCI at ≥72 hours post-administration (or sooner if associated with symptoms of diarrheal illness up to Day 28)		

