A participant will be considered as showing clinical diarrheal illness if diarrhea is observed with at least two diarrheal bowel events within 24 hours on at least two days during the observation period beginning after the ABO809 administration (Day 1) and ending on Day 28 (see Section 8.3.2)

Resolution of diarrheal illness from Cryptosporidium infection requires ≥ 2 consecutive days with no diarrheal stools (stool sample grades 1 or 2).

Participants will be monitored daily for infection (parasitological evaluation) and diarrheal illness (clinical evaluation) during the domicile period. The monitoring of symptoms will continue in the outpatient setting with the collection of information via the CHIM diary and Safety Follow-Up Calls. Participants will provide a health and stool update daily from Day 1 through 28 in the CHIM diary. Safety Follow-Up Calls will occur on Days 35, 42, 49, and 56.

The primary endpoint is *Cryptosporidium* infection as indicated by detection of oocysts in fecal samples by EIA CCI ≥72 hours following an oral administration of ABO809 (or sooner if associated with symptoms suggestive of diarrheal illness). Secondary endpoints include characterization of diarrheal illness, safety and tolerability.

Figure 3-1 Study Design

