8.3.2 Evaluation of Clinical Signs and Symptoms

To assess the incidence and characteristics of cryptosporidiosis, the signs and symptoms associated with cryptosporidiosis will be monitored as described in the Assessment Schedule (Table 8-1).

Onset, progression, improvement and resolution of signs and symptoms associated with *Cryptosporidium* infection will be recorded in the eCRF at Baseline and approximately

every 8 hours during the Inpatient Follow-Up period, at Outpatient Follow-Up visits/Safety Follow-Up Calls and at any unscheduled visits. Symptoms of cryptosporidiosis will be AEs; these and any SAEs will be recorded as such (see Section 10).

Diarrhea is defined as at least one stool sample grading 3-5 on the Stool Grading System (see Section 16.1) in one day. Grades 3-5 stools are defined as thick liquid diarrhea taking the shape of the container, opaque watery, rice water or clear watery stools. Diarrhea will be further characterized by measuring the form of the stool, the total weight of stool, the number and frequency of diarrheal episodes and the time to resolution of diarrheal illness.

Diarrhea data will be collected as follows: onset, progression, total stool output (weight in grams) and severity of diarrhea (Grading will be assessed using the U.S. Food and Drug Administration's (FDA) "Toxicity Grading Scale for Healthy Adult and Adolescent Volunteers Enrolled in Preventive Vaccine Clinical Trials (2007)"; the worst grade each day will be recorded).

Data on other gastrointestinal symptoms associated with *Cryptosporidium* infection will be recorded in the eCRF as follows: presence (yes/no), onset, severity (mild, moderate, severe), therapeutic intervention (yes/no; if yes what) and progression (ongoing, resolved). These gastrointestinal symptoms include:

- abdominal pain or discomfort
- abdominal tenderness
- abdominal rebound
- abdominal distension
- fecal urgency
- nausea/vomiting
- flatulence
- tenesmus
- poor appetite
- presence of blood
- fever

Since nausea/vomiting, diarrhea, headache, fatigue, and myalgia are listed in the US FDA "Toxicity Grading Scale for Healthy Adult and Adolescent Volunteers Enrolled in Preventive Vaccine Clinical Trials (2007)" these symptoms should be graded according to provided definitions in the guidance document (compare Section 10.1.1).

Other symptoms the Investigator considers potentially related to ABO809 administration will also be recorded in the eCRF as free text.

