A participant will be considered as showing clinical diarrheal illness if diarrhea is observed on at least two days during the observation period beginning after the ABO809 administration (Day 1) and ending on Day 28.

Resolution of diarrheal illness from Cryptosporidium infection requires ≥ 2 consecutive days with no diarrheal stools (stool sample grades 1 or 2).

8.3.2.1 **CHIM Diary**

Participants will provide a health and stool update daily from Day 1 to Day 28 in a Participant CHIM Diary. Any clinical symptoms, and/or diarrheal episodes associated with *Cryptosporidium* infection should be recorded. The Diary will be submitted to the site at Day 28.

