12.8.2 Secondary endpoint(s)

Assuming the true incidence of clinical symptoms is 70%, there is at least 80% chance to claim that the incidence is at least 53% with a sample size of 30 participants, and 48% with a sample size of 20 participants, and 58% with a sample size of 60 participants. The calculation is based on the 1-sided 80% exact confidence interval.

13 Ethical considerations and administrative procedures

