2.5.2 Statistical hypothesis, model, and method of analysis

The number and percentage of participants with clinical symptoms (diarrheal and associated symptoms) (by Day 10 (inclusive) and Day 28) and with *Cryptosporidium* infection up to Day 28 will be tabulated by treatment group. The 2-sided 80% exact confidence interval of the clinical symptom rate will be reported by treatment group.

Frequency and percentage will be presented for categorical data such as grading of stool, evidence of occult blood in stool and number of diarrhea episodes. Mean, standard deviation, median, minimum, and maximum will be presented for continuous data such as stool weight. Overlaying individual stool weight-time profiles will be generated.

Time to onset and time to resolution of infection and diarrheal illness will be summarized using Kaplan-Meier graphs with separate lines by treatment group. Median time to event for each treatment group will be estimated along with 90% confidence intervals.

Duration of infection and diarrheal illness will be summarized by treatment group.

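### Clinical diarrheal illness has two definitions, and the incidence analysis is attached to clinical symptoms over an unsettled window, so the illness rate to be reported is not determined

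*Protocol*

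**What the plan says.** **Endpoint.** Protocol Table 2-1 lists, under the first secondary objective, "Presence of clinical diarrheal illness by Day 10 (inclusive) and Day 28". SAP Table 1-1 repeats it.

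**Definition.** Protocol Section 3 calls a participant ill "if diarrhea is observed with at least two diarrheal bowel events within 24 hours on at least two days" up to Day 28, and refers the reader to 8.3.2. SAP 2.1.1.1 uses the same rule. Protocol 8.3.2 says: "A participant will be considered as showing clinical diarrheal illness if diarrhea is observed on at least two days". The same section sets the threshold for a diarrhea day: "Diarrhea is defined as at least one stool sample grading 3-5 on the Stool Grading System".

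**Analysis.** Protocol 12.5 names clinical symptoms as the secondary variable and cites 8.3.2. Protocol 12.5.1 gives the proportion and a one-sided 80% lower limit for clinical symptoms by Day 10 and Day 28, then adds: "The clinical symptoms are defined as diarrheal and associated gastrointestinal symptoms, evaluated from symptom onset up to Day 10". SAP 2.5.2 tabulates "The number and percentage of participants with clinical symptoms (diarrheal and associated symptoms") and puts a two-sided 80% exact interval on that rate. The precision statement in Protocol 12.8.2 starts from the same variable: "Assuming the true incidence of clinical symptoms is 70" percent.

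**Window.** Protocol 12.4 says of the primary endpoint: "The 10 day observation window may be extended as described in Section 4.1". Protocol 12.5.1 says the same of clinical symptoms. Table 2-1 and SAP 2.4.1 end the primary endpoint at Day 10.

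**Dose review.** Protocol 6.5.1 sets a target of about 60%-70% with diarrheal illness and points to Section 3 for the definition. It also lists the incidence of clinical symptoms among the data to be reviewed.

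**The concern.** The illness rate is one of the two results that show whether the challenge model is usable. A reader of the report should be able to say which participants count, over which days, and that the same rule was applied at each dose review. The text does not settle this. Two programmers working from different sections could produce different rates from the same data, and in an open-label study the choice could be made after the results are known.

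The broader variable is also the more exposed one. Protocol 4.1 accepts a residual risk of reporting bias for anticipated symptoms such as abdominal pain and nausea, while treating diarrhea as little affected.

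The window sentence raises a separate issue. If it were applied to the primary endpoint, the length of observation would depend on whether a participant still had symptoms.

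**Working it through.** **1. Which variable each place uses**

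| Place | Variable | Rule or window |
|---|---|---|
| Protocol synopsis | diarrheal illness | no definition or time point |
| Protocol Table 2-1, SAP Table 1-1 | clinical diarrheal illness | Day 10 and Day 28 |
| Protocol Section 3, SAP 2.1.1.1 | clinical diarrheal illness | 2 events in 24 h, on at least 2 days, to Day 28 |
| Protocol 8.3.2 | clinical diarrheal illness | 1 grade 3-5 stool a day, on at least 2 days, to Day 28 |
| Protocol 6.5.1, target | diarrheal illness | per Section 3 |
| Protocol 6.5.1, data reviewed | clinical symptoms | to Day 10 |
| Protocol 12.5.1 | clinical symptoms | Day 10 and Day 28, then defined to Day 10, extendable |
| Protocol 12.8.2 | clinical symptoms | 70% assumed |
| SAP 2.5.2 | clinical symptoms | Day 10 and Day 28 |

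Anyone who meets the Section 3 rule also meets the 8.3.2 rule, but not the reverse. The direction of the difference is therefore certain: the 8.3.2 rate cannot be the lower one.

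**2. The window**

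Section 4.1 discharges participants on Day 10 if diarrheal symptoms have resolved and otherwise prolongs the stay. While domiciled, up to 3 stools a day are tested (8.3.1). After discharge, participants bring stools from the 24 hours before each visit on Days 14, 17, 21, 24 and 28 (Table 8-1, footnote 4). An extended window would give symptomatic participants more chances to test positive. Each participant reclassified would move the rate by 1/30 = 3.3 points at n=30. The documents give no basis for how many that would be.

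**3. The plan's own precision figures**

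Inputs from 12.8.2: true rate 0.70, at least 80% chance, one-sided 80% exact interval. Take the largest x with P(X ≥ x | n, 0.70) ≥ 0.80; the lower limit is the 20th percentile of Beta(x, n − x + 1).

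| n | x | P(X ≥ x) | Lower limit | Stated |
|---|---|---|---|---|
| 20 | 12 | 0.887 | 48.1% | 48% |
| 30 | 19 | 0.841 | 54.0% (53.99) | 53% |
| 60 | 39 | 0.838 | 58.8% | 58% |

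The figures reproduce after rounding down, so the arithmetic is sound. What is unclear is which variable the 70% describes; it equals the top of the 60%-70% diarrheal illness target. By the same method, for n = 20/30/60, an assumed true rate of 50% gives limits of 29/34/39%, and 29% gives 12/16/18%.

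**4. Illustration: symptoms against diarrheal illness**

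Protocol 4.5 cites one study with n=7 at 1000 or more oocysts: 71% with enteric symptoms and 29% with diarrheal illness. 5/7 = 71% and 2/7 = 29%. The text words the 29% as a share of those with symptoms, but no count out of 5 gives 29%, so I read it as 2 of 7. The gap is 71 − 29 = 42 points. Assuming these rates, the chance that a cohort of 10 shows at least 6 (60%) is 86.6% at 0.71 and 4.0% at 0.29.

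**5. Illustration: Section 3 against 8.3.2**

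Assume Poisson diarrheal stools with mean λ per calendar day over 3 illness days. A day qualifies with probability p = 1 − e^(−λ) under 8.3.2 and p = 1 − e^(−λ)(1 + λ) under Section 3. At least 2 of 3 days qualify with probability 3p² − 2p³.

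| λ | p, 8.3.2 | Meets 8.3.2 | p, Section 3 | Meets Section 3 |
|---|---|---|---|---|
| 1 | 0.632 | 69% | 0.264 | 17% |
| 2 | 0.865 | 95% | 0.594 | 64% |

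Over means of 1 to 3 and 2 to 4 days, the shares run from 40% to 100% under 8.3.2 and from 7% to 97% under Section 3.

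**The case against.** Much can be said for the plan. The synopsis promises the diarrheal illness proportion in the same form as the infection proportion. The SAP, which the protocol names as the place for analysis detail, has a single definition matching Section 3. SAP 2.5.1 derives presence of illness from diarrhea data and treats other gastrointestinal symptoms in a separate paragraph. The dose criterion points to Section 3. SAP 2.5.2 asks for both Day 10 and Day 28, and Table 2-1 and SAP 2.4.1 fix the primary endpoint at Day 10. The study is descriptive, with no hypothesis test.

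These points rule out several stronger inferences that a reader might draw:

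- That diarrheal illness will get no proportion or interval, or that the secondary objective will go unanswered. The synopsis says otherwise.
- That flatulence or poor appetite alone would count. This is only one reading of diarrheal and associated symptoms. Both items come from the 8.3.2 list; the associated symptoms named in 12.5.1 include neither.
- That dose decisions will rest on a symptom rate. The criterion itself is on illness per Section 3. Further interim detail (Protocol 4.4 and 12.7, SAP 2.12) is not available in the public text, so it cannot be checked.
- That the primary infection rate is biased. Section 4.1 prolongs the stay and does not itself set an endpoint window.

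What remains is the inconsistency. The synopsis gives neither a definition nor a time point, and its commitment is not carried into 12.5.1 or SAP 2.5.2. SAP 2.5.1 lists descriptive measures and stops short of a rule for presence. SAP Section 4 reports no change from the protocol, so the SAP does not openly replace 8.3.2 or the extension sentences.

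**Conclusion.** The point holds as an inconsistency that leaves the reported illness rate undetermined. The two definitions conflict. The sections that assign the proportion, interval and precision statement name a different variable from the endpoint table. Protocol 12.5.1 contradicts itself on Day 10 and Day 28, and the extension sentences conflict with the fixed Day 10 primary endpoint.

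The size cannot be estimated from the documents. The 42-point gap rests on 7 participants, an inferred denominator, and a definition of diarrheal illness in the cited study that the documents do not give. Table 4-1 shows diarrhea incidence from 0-38% in one study to 52-86% in another. The Poisson figures rest on assumed stool rates. They also count by calendar day, whereas the Section 3 wording could span midnight, which would narrow the gap. Only the direction is firm: Section 3 is the narrower rule. The precision figures in 12.8.2 are arithmetically correct for a rate of 70%, whichever variable that rate describes.

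**What to change.** - Reconcile Protocol Section 3, Protocol 8.3.2 and SAP 2.1.1.1 to one definition of clinical diarrheal illness. The SAP and the dose criterion currently follow Section 3. Because the definition feeds the dose review, which clinical rule is right is for the sponsor and the investigator to settle.
- Reconcile the two terms within Protocol 6.5.1 with that definition.
- In Protocol 12.5, 12.5.1 and 12.8.2 and SAP 2.5.1 and 2.5.2, name clinical diarrheal illness by Day 10 and by Day 28 as the tabulated variable with its exact interval. Tabulate other gastrointestinal symptoms separately.
- State that the 70% in 12.8.2 refers to that variable, or revise it.
- Delete the extension sentences in Protocol 12.4 and 12.5.1, so that the primary window ends at Day 10 for everyone. Later cases are counted in the Day 28 endpoints.

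The cost is wording in the two documents, with no new data. The reported illness rate may be lower than a symptom rate would have been.

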12.5.2 Safety endpoints

For all safety analyses, the safety set will be used. All listings and tables will be presented by treatment group.

Safety summaries (tables, figures) include data from Day 1 until the EOS with the exception of Baseline data which will also be summarized where appropriate (e.g. change from baseline summaries). In addition, a separate summary for death including on-treatment and post treatment deaths will be provided.

Adverse events

The number (and percentage) of participants with adverse events will be summarized in the following ways:

- by Primary system organ class and preferred term
- by Primary system organ class and preferred term and maximum severity

Separate summaries will be provided for ABO809 related AEs, SAEs, AESIs and deaths.

A participant with multiple AEs within a primary system organ class is only counted once towards the total of the primary system organ class.

Vital signs

All vital signs data will be listed by treatment group, participant, and visit/time and if ranges are available, abnormalities (and relevant orthostatic changes) will be flagged. Summary statistics will be provided by treatment and visit/time.

ECG findings

For ECG parameters, summary statistics for baseline value, actual assessment values, and change from baseline values will be presented by time of measurement. All ECG data will be listed; notably abnormal values will be flagged, and the overall interpretation of abnormality will be presented.

Clinical laboratory evaluations

Clinical laboratory data will include chemistry, hematology and urinalysis results up to EOS.

All laboratory values will be converted into International System of Units (SI) units. If grades are not defined by the Toxicity Grading Scale for Healthy Adult and Adolescent Volunteers Enrolled in Preventive Vaccine Clinical Trials (2007), results will be graded by the low/normal/high classifications based on laboratory normal ranges. Continuous laboratory data will be summarized by presenting summary statistics of raw data and change from baseline values (means, medians, standard deviations, ranges) by time point.

12.6 Analysis of exploratory endpoints

Commercially Confidential Information

12.7 Interim analyses

12.8 Sample size calculation

12.8.1 Primary endpoint(s)

Approximately 10 participants in each cohort will be enrolled to receive ABO809. The sample size is driven by practical reasons. Assuming the true incidence of infection is 90%, there is at least 80% chance to claim that the incidence is at least 78% with a sample size of 30 participants, and 74% with a sample size of 20 participants, and 81% with a sample size of 60 participants. The calculation is based on the 1-sided 80% exact confidence interval.

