 To evaluate the time to onset and resolution of Cryptosporidium infection in participants who developed an infection following an oral administration of ABO809 	 Detection of fecal shedding of C. parvum oocysts by EIA CCI up to 28 days after administration of ABO809 		
	 Time to onset and time to resolution of Cryptosporidium infection following an oral administration of ABO809 		
 To assess the safety and tolerability of ABO809 	 Adverse events, vital signs, ECG findings, safety laboratory assessments including chemistry, hematology, and urinalysis results up to and including the Day 28 visit 		
	 Adverse events of special interest by telephone follow-up after Day 28 through 12 months after ABO809 administration 		

Objective(s) Endpoint(s)

Commercially Confidential Information

3 Study design

This Phase 1 Cryptosporidium CHIM study employs a single-center, open-label design to characterize the incidence of infection and associated symptoms following the administration of single doses of *C. parvum* oocysts (ABO809).

The study will enroll healthy volunteers in cohorts of approximately 10 participants who will receive ABO809 on the same day. A dose level group will receive the same ABO809 dose and can be comprised of multiple cohorts. The first dose level group will start with a cohort of 10 participants who will receive ABO809 at a dose of 1x10⁴ oocysts. The study will continue to enroll participants in the same dose level group if the desired incidences of infection and diarrheal illness are observed, up to a total of approximately 30 participants. If the desired incidences of infection and diarrheal illness are not observed, a new dose level group, receiving ABO809 at a dose of 1x106 oocysts, may be initiated. If needed to optimize the model, intermediate ABO809 doses may be evaluated (see Section 6.5).

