12.1 Analysis sets

For all analysis sets, participants will be analyzed according to the dose of ABO809 (*C. parvum* oocysts, also referred to as "treatment").

The safety analysis set will include all participants that received ABO809.

The PD analysis set includes all participants with available safety, parasitological and clinical data and with no protocol deviations with relevant impact on PD data.

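### The n=60 precision figures in Protocol 12.8.1 and 12.8.2 are computed correctly but do not apply to the by-dose analysis, in which a dose level is planned for about 30 participants

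*Protocol*

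**What the plan says.** **Sample size.** Protocol 12.8.1 begins "Assuming the true incidence of infection is 90" per cent and continues "there is at least 80% chance to claim that the incidence is at least 78% with a sample size of 30 participants". It then gives 74% for 20 participants, "and 81% with a sample size of 60 participants". Protocol 12.8.2 begins "Assuming the true incidence of clinical symptoms is 70" per cent and gives 53% for 30 participants, 48% for 20, "and 58% with a sample size of 60 participants". Both sections use the same interval: "The calculation is based on the 1-sided 80% exact confidence interval". Neither says whether n counts participants at one dose or at all doses.

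**Enrolment.** Protocol Section 3 starts with 10 participants at the first dose level and continues at that level, if the desired incidences are seen, "up to a total of approximately 30 participants". The study total is 30, rising to a maximum of about 60. The same section mentions additional cohorts in connection with a change of dose.

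**Analysis.** Protocol 12.1 says that "participants will be analyzed according to the dose of ABO809". Protocol 12.5.1 reports the secondary limits by treatment, which here means dose. SAP 2.4.2 tabulates the primary infection rate by treatment, and SAP 2.5.2 does the same for the secondary rates. SAP 2.1 also plans a pooled analysis of key outcomes over all cohorts. SAP 2.1.1 links pooled analyses to the treatment group name used without the cohort number.

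**Interval.** Protocol 12.4.1 and 12.5.1 report a one-sided 80% exact lower limit. SAP 2.4.2, 2.5.2 and 5.5.1 specify a two-sided 80% exact interval. SAP Section 4 declares no change to the protocol analyses.

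**The concern.** The sample-size sections are where a reader learns how precisely the model's infection and illness rates will be known. The figure that matters is the one for a single dose, because a later study would use a chosen dose. The n=60 figures are the most favourable of the six and carry no label. They can therefore be taken as precision for a selected dose, although the plan puts only about half that number at any one dose.

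The interval adds to this. All six figures rest on a one-sided 80% limit, but the SAP will report the lower end of a two-sided 80% interval, which is lower for the same data.

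**Working it through.** **Inputs.** The true incidences are 0.90 for infection (Protocol 12.8.1) and 0.70 for symptoms (12.8.2). The interval is one-sided 80% exact, and the required chance is at least 80%. A dose level has about 30 participants and the study has at most about 60 (Protocol Section 3). So 60 / 30 = 2, and full enrolment means at least two dose levels.

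**Method.** For each n, take the largest x with P(X ≥ x) ≥ 0.80, where X is Binomial(n, p). The claimable limit is the Clopper-Pearson lower limit, the α quantile of Beta(x, n − x + 1). Use α = 0.20 for the one-sided 80% limit and α = 0.10 for the lower end of a two-sided 80% interval.

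**Step 1: reproduce the plan's figures (α = 0.20).**

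| Endpoint | n | x | P(X ≥ x) | Limit | Stated |
|---|---|---|---|---|---|
| Infection, p = 0.90 | 20 | 17 | 86.7% | 74.1% | 74% |
| Infection | 30 | 26 | 82.5% | 78.6% | 78% |
| Infection | 60 | 52 | 85.8% | 81.6% | 81% |
| Symptoms, p = 0.70 | 20 | 12 | 88.7% | 48.1% | 48% |
| Symptoms | 30 | 19 | 84.1% | 54.0% | 53% |
| Symptoms | 60 | 39 | 83.8% | 58.8% | 58% |

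All six agree once rounded down.

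**Step 2: apply the n=60 limits to one dose level of 30 (α = 0.20).**

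- Infection, limit of at least 81%: 26/30 gives 78.6%, which is too low. 27/30 gives 82.4%, and P(X ≥ 27) = 64.7%.
- Symptoms, limit of at least 58%: 20/30 gives 57.4%, which is too low. 21/30 gives 60.8%, and P(X ≥ 21) = 58.9%.

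Neither reaches 80%. In stated figures, n=60 is more favourable than n=30 by 81 − 78 = 3 points and 58 − 53 = 5 points.

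**Step 3: what n=60 needs if doses are pooled.** The figures then require the same incidence at every dose. The rates below are assumptions chosen only to show sensitivity, with 30 participants at each of two doses:

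| Assumed true rates | Pooled limit | Chance of reaching it |
|---|---|---|
| Infection 80% and 90% | ≥ 81% (52/60) | 44% |
| Infection 70% and 90% | ≥ 81% (52/60) | 12% |
| Symptoms 60% and 70% | ≥ 58% (39/60) | 56% |

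**Step 4: use the SAP's two-sided 80% interval (α = 0.10).**

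| Endpoint | n | Stated limit | Chance of reaching it | Limit reached with ≥ 80% chance |
|---|---|---|---|---|
| Infection | 20 | 74% | 67.7% | 69.6% |
| Infection | 30 | 78% | 64.7% | 75.1% |
| Infection | 60 | 81% | 75.2% | 79.2% |
| Symptoms | 20 | 48% | 77.2% | 43.3% |
| Symptoms | 30 | 53% | 73.0% | 50.0% |
| Symptoms | 60 | 58% | 66.9% | 56.0% |

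None of the six stated limits keeps an 80% chance on the interval that the SAP will report.

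**The case against.** The strongest reply is that nothing is miscalculated. Each figure is conditional on a stated n, and the n=20 and n=30 figures stand beside it. The arithmetic part of this is right, but it does not supply the missing statement of which analysis has n=60.

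A reader might go further and infer that n=60, or limits of 81% and 58%, cannot be reached. The documents do not support that, for three reasons:

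- SAP 2.1 plans a pooled analysis of key outcomes over all cohorts. If it crosses doses, n can be about 60. SAP 2.1.1 can be read as pooling cohorts only within a dose, so the scope is unclear rather than excluded.
- The 30 is approximate. Protocol 9.1.1.1 allows later cohorts to be enlarged, and Section 3 does not say that a dose change is the only route to more cohorts. Thirty is the planned size of a dose level, not a hard limit.
- A limit of 81% or 58% can be observed at n=30. What is lost is the stated 80% assurance.

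It is also fair to say that a common incidence is not refuted. Protocol 4.2 cites complete infection above 10³ oocysts in seronegative participants and no clear relation between dose and clinical illness. But the assumption is unstated. It is also least secure where it is needed, because the design moves to another dose when the desired incidences are not observed.

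No test or decision threshold uses 81% or 58%, and 12.8.1 attributes the sample size to practical reasons. This limits the consequence to how precision is understood. Parts of the interim and SAP sample-size sections are redacted, so any scope wording there could not be checked.

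A reader might also compute the probability that one dose level reaches 30. Protocol 6.5.1 does not support a firm figure: its criteria are approximate and are weighed with the totality of data, and the dependence between infection and illness is not given.

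**Conclusion.** The concern holds as a matter of scope, not of arithmetic. The n=60 figures are correct for 60 participants who share one incidence, but they are not a property of the planned by-dose estimate. For one dose level of 30, the one-sided limits with at least 80% chance are 78.6% and 54.0%, and the chance of reaching the n=60 limits is 64.7% and 58.9%. These results assume true incidences of 90% and 70%, 30 evaluable participants at one dose, and independent binomial outcomes. If the two-sided 80% interval is kept, the per-dose limits fall further, to 75.1% and 50.0% at n=30.

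**What to change.** 1. In Protocol 12.8.1 and 12.8.2, either delete the n=60 figures or label them as all doses pooled, with a common incidence assumed, and as distinct from the by-dose primary analysis.
2. In SAP 2.1 and 2.1.1, state whether pooled analyses cross doses or combine cohorts only within a dose.
3. Reconcile the protocol's one-sided 80% limit with the SAP's two-sided 80% interval, and record any change in SAP Section 4.
4. Restate the per-dose figures for the interval chosen. If one-sided, the n=20 and n=30 figures stand. If two-sided, they become about 69.6% and 75.1% for infection, and about 43.3% and 50.0% for symptoms, at n=20 and n=30 respectively.

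Enrolment and conduct do not change. The cost is a less favourable stated precision. The best per-dose figures become 78% and 53% with the one-sided limit, or about 75% and 50% with the two-sided interval.
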